6.5.1 Permitted Medicines

Any medications that are considered necessary to protect subject welfare and will not interfere with the study medication may be given at the Investigator's discretion.

Healthy Subjects

Occasional use of paracetamol/acetaminophen or ibuprofen (not > 500 mg per day) within 7 days before IMP administration is allowed.

Hepatic Impaired Subjects

A stable regimen of other prescribed drugs and vitamins is allowed.

6.5.2 Prohibited Medicines

All Subjects

Antacids, H2-blockers, and proton pump inhibitors might affect the absorption of tepotinib. H2-blockers or proton pump inhibitors should be stopped 5 days prior Day 1, until Day 2. Antacids should not be taken 1 hour before IMP administration until 2 hours after IMP administration.

Healthy Subjects

Use of any medication, including multi-vitamin preparations, received within 10 days prior to Day 1, or within 6 times the elimination half-life, whichever is the longest, except the occasional use of paracetamol/acetaminophen or ibuprofen (> 500 mg per day is prohibited) within 7 days before Day 1 until the End of Study visit.

Hepatic Impaired Subjects:

Concomitant medication inducing or inhibiting P-gp, BCRP, OCT1, OCT2, MATE1, or MATE2 should be stopped from 5 days prior to Day 1 until the End of Study visit.

Current intake of any drug with dose dependent hepatotoxicity, such as paracetamol/acetaminophen > 500 mg per day is not allowed.

A change in the medication (prescribed by a physician or over-the-counter) used other than for hepatic insufficiency within 7 days prior to Day 1 is not allowed.

The use of nonpermitted concomitant medications for any reason during the study must result in withdrawal of the subject from the study. However, any medications that are considered necessary for the subject's wellbeing may be given at the discretion of the Investigator.

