5.5 Criteria for Subject Withdrawal

5.5.1 Withdrawal from Investigational Medicinal Product Administration

Not applicable since the IMP is administered only once in the study.

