5.5.2 Withdrawal from the Study

Subjects may withdraw from the study at any time without giving a reason.

A subject must be withdrawn from the study if any of the following occur during the study:

- Subject withdrew consent
- Participation in another clinical study during the duration of this study
- Use of nonpermitted concomitant medications, as defined in Section 6.5. However, any medications that are considered necessary for the subject's wellbeing may be given at the discretion of the Investigator
- Protocol noncompliance judged as significant by the Investigator, including noncompliance to the required study considerations (eg, food/diet requirements)
- Subject lost to PK sampling
- Any event that unacceptably endangers the safety of the subject.

If there is a medical reason for the withdrawal, the subject will remain under the supervision of the Investigator until satisfactory health has returned or care has been transferred to the subject's general practitioner or to a hospital consultant.

In case of premature withdrawal from the study, the assessments scheduled for the End of Study visit should be performed, if possible, with the focus on the most relevant assessments (see Table 1). Regardless, the appropriate electronic case report form (eCRF) section should be completed.

Subjects who are withdrawn after IMP administration and are not evaluable will be replaced, as discussed by the Investigator and Medical Responsible of the Sponsor.

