7.1.3 End of Study Visit/Early Termination Visit

Healthy subjects will partake in the End of Study visit on Day 15 and hepatic impaired subjects will partake in the End of Study visit on Day 22. Assessments at the End of Study visit are specified in the Schedule of Assessments for Part 1 and Part 2 (Table 1). Subjects who discontinue from the study for any reason prior to the End of Study visit must undergo an Early Termination visit immediately upon discontinuation. Assessments at the Early Termination visit are the same as for the End of Study visit.

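### Withdrawing subjects from the study for nonpermitted medication after the only dose ends data collection without reducing exposure, and the wellbeing allowance leaves unclear who must go

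*Protocol*

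**What the plan says.** Section 6.5.2 makes withdrawal mandatory: "The use of nonpermitted concomitant medications for any reason during the study must result in withdrawal of the subject from the study". The next sentence reads "However, any medications that are considered necessary for the subject's wellbeing may be given at the discretion of the Investigator". Section 5.5.2 has the same pair. Its list of events after which a subject must be withdrawn includes "Use of nonpermitted concomitant medications, as defined in Section 6.5", followed within the same bullet by the wellbeing allowance. That list also includes "Subject lost to PK sampling". Section 6.5.1 separately permits welfare medication, on condition that it does not interfere with the study drug.

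On withdrawal from dosing, Section 5.5.1 says "Not applicable since the IMP is administered only once in the study". Under Section 7.1.3, a subject who discontinues before the End of Study visit "must undergo an Early Termination visit immediately upon discontinuation", with the End of Study assessments. No section provides for further scheduled PK samples or visits after that.

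On replacement, Section 5.5.2 says "Subjects who are withdrawn after IMP administration and are not evaluable will be replaced", after discussion between the Investigator and the Sponsor. Section 8.1 limits replacement to drop-outs without an evaluable PK profile. The PK Analysis Set (Section 8.4) needs at least one postdose measurement and excludes important deviations or events that may affect PK.

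**The concern.** In a multiple-dose trial, withdrawal for a prohibited drug at least stops further exposure. Here the dose has already been taken, so leaving the study only stops observation. The analysis does not need this protection: concomitant medication is recorded (Section 6.5) and the PK Analysis Set already screens for deviations that matter. Collected samples can be excluded later; samples never drawn cannot be recovered.

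At stake are the primary endpoints AUC0-t and AUC0-infinity, the metabolite AUCs (secondary endpoints), and part of the post-dose safety record, in groups of six. The two adjoining sentences also allow two sites to handle the same case differently: one withdraws the subject and the other keeps sampling. One subject is 1/6 = 17% of a group.

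**Working it through.** **The plan's own figure.** Section 8.1 claims 80% power with 6 per group at two-sided 0.05, for differences of 44% (AUC0-t, CV 20.4%) and 50% (Cmax, CV 22.8%). I used a two-sample t-test on the log scale with SD = sqrt(ln(1 + CV²)) and 10 df. For AUC0-t the SD is 0.2019, the difference is ln(1.44) and power is 80.4%. For Cmax the SD is 0.2251, the difference is ln(1.50) and power is 80.2%. The claim reproduces, and this point does not disturb it. If one subject in a group were lost and not replaced (5 against 6), power would be 75.6% and 75.4%. With two lost (4 against 6), it would be 68.9% and 68.7%.

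**What an early stop costs.** Inputs from the protocol:
- Sampling times of 72 h (Day 4), 168 h (Day 8), 216 h (Day 10), 336 h (Day 15) and 504 h (Day 22, impaired subjects only), from Table 1.
- The rule in Section 7.5.2 that AUCextra% above 20% flags the terminal rate constant and everything derived from it as invalid.
- The M506 half-life: geometric mean 93 h, range 66 to 145 h, from 4 subjects (Sections 3.2 and 5.2.3). The two metabolites analysed are its enantiomers.

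Assumption: the protocol gives no parent half-life, so I take 30 to 93 h. The lower end is assumed and the upper end is the M506 mean.

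For a mono-exponential tail, the unobserved share after stopping at T is 2^(−T/h), where h is the half-life. It falls to 20% at T = h × log2(5) = 2.32h.

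| Half-life | Stop at 72 h | Stop at 168 h | Time to reach 20% |
|---|---|---|---|
| 30 h (assumed) | 19% | 2% | 70 h |
| 66 h (M506 low) | 47% | 17% | 153 h |
| 93 h (M506 mean) | 59% | 29% | 216 h |
| 145 h (M506 high) | 71% | 45% | 337 h |

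Put the other way, the 20% limit is breached at a 72 h stop only if the half-life exceeds 72/2.32 = 31 h, and at a 168 h stop only if it exceeds 168/2.32 = 72 h.

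**Effect on a group mean.** If one subject of six is truncated and stays in the analysis, the group geometric mean falls by about 1 − (1 − share)^(1/6), relative to complete profiles. At 72 h this is 1 − 0.81^(1/6) = 3% to 1 − 0.415^(1/6) = 14%. At 168 h it is under 1% to about 5%. The direction is towards lower apparent exposure in whichever group is affected.

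**Safety time.** A withdrawal at discharge on Day 4 forgoes 22 − 4 = 18 days of scheduled follow-up for an impaired subject and 15 − 4 = 11 days for a healthy one.

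The tail formula ignores any distribution phase and the late M506 peak (median 24 h), so all shares are approximate.

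**The case against.** The wellbeing sentence can be read as an exception to withdrawal, especially in Section 5.5.2, where it sits inside the withdrawal bullet, and Section 6.5.1 lists non-interfering welfare medication as permitted. That is a fair reading, so the rule need not catch every case. But Section 6.5.2 says withdrawal applies whatever the reason, and neither section states that such a subject stays.

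A reader might infer that the rule selects more stable cirrhotic subjects into the impaired groups. The protocol does not show this. The broadest ban, on nearly all medication until End of Study, falls on healthy subjects (exclusion criterion 15). Impaired subjects may keep a stable regimen, and the ban on changed medication covers only the 7 days before Day 1. Replacement can occur in any group and only for non-evaluable subjects. Selection is therefore possible but not built in. For any one subject, truncation and replacement are also alternatives: a subject kept in the analysis is not replaced, and a replaced one does not bring in a truncated AUC.

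A reader might also infer that safety follow-up stops. It does not. The Early Termination visit repeats the End of Study assessments. Section 5.5.2 adds "If there is a medical reason for the withdrawal, the subject will remain under the supervision of the Investigator until satisfactory health has returned"; handover to another physician is the stated alternative. Ongoing serious events are followed up (Section 7.4.1.6), and related ones are reported whenever they occur (Section 7.4.1.3).

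Finally, the larger truncation figures use a metabolite half-life, while the primary endpoints concern the parent. At 30 h even a 72 h stop stays just inside the limit. That stands, and it confines the AUCextra% concern mainly to the metabolites.

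**Conclusion.** The point holds in a limited form. Two sections require withdrawal from the study when there is no dosing left to stop, and following them gives up PK samples and safety visits that could simply continue.

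The consequences are conditional. AUC0-t is truncated if the subject remains in the PK Analysis Set. A breach of the 20% limit is likely for the metabolites after a first-week withdrawal: at the M506 mean half-life, sampling to about Day 10 is needed. For the parent, a breach occurs only if withdrawal is early or the half-life is long. Safety follow-up is cut short.

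The size rests on a mono-exponential tail, an assumed parent half-life and an illustrative loss of one subject in six, because the protocol gives no expected frequency. The sample-size calculation is sound. Separately, and whatever view is taken of the design, the wellbeing sentences conflict with mandatory withdrawal and must be reconciled.

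**What to change.** In Sections 5.5.2 and 6.5.2, replace mandatory withdrawal by three steps:
- Record the use of nonpermitted medication as a protocol deviation.
- Continue the PK sampling and safety visits already scheduled, to Day 15 or Day 22, unless the subject withdraws consent or the Investigator judges that safety requires otherwise.
- Decide inclusion in the PK Analysis Set by the existing deviation rule, before database lock.

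For subjects lost to PK sampling who are willing to attend, keep the scheduled safety visits. Reconcile the wellbeing sentences in 5.5.2 and 6.5.2 with each other and with the condition in 6.5.1, stating whether such a subject remains in the study. Which medicines are permitted is a clinical matter for the Sponsor and is not addressed here.

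The cost is a wording amendment, with no visits beyond those in Table 1. The downside is case-by-case review of a few profiles. Subjects excluded for an interacting drug may still need replacement, so the change reduces the loss but does not remove it.

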6.5.3 Other Interventions

All Subjects

Subjects are not allowed to smoke > 10 cigarettes per day, or equivalent use of other forms of nicotine (ie, patches, gum, chewing tobacco, vaping) for the duration of the study.

Subjects are required to refrain from alcohol intake during confinement. Subjects should not consume more than 14 (women) or 21 (men) units of alcohol a week (unit = 1 glass of wine (125 mL) = 1 measure of spirits = $\frac{1}{2}$ pint of beer).

Subjects will receive the IMP after they have completed a standard breakfast. Drug administration is 30 minutes after start of the intake of a standard breakfast with 240 mL of water. Subjects should eat this meal within 25 minutes or less. The subject will remain fasting for 4 hours after the breakfast, after which a standardized lunch will be served. The standard breakfast will contain approximately 500 calories and will be balanced in macronutrients (approximately 50% carbohydrates, 25% protein, and 25% fat). The menu must be approved by the Sponsor. The subject will be expected to eat the entire meal. The percentage consumed will be recorded for all subjects. A deviation will be recorded if the subject eats less than 90% of the meal. Subjects will not be excluded from dosing if they are unable to complete the meal in full.

6.5.4 Special Precautions

This study will be performed at 2 hospital-based, inpatient, Phase 1 research centers with personnel trained in basic or immediate life support. Equipment and other agents (ie, epinephrine and prednisolone equivalents, etc.) will be available at the study center in case of allergic reactions.

6.5.5 Management of Specific Adverse Events or Adverse Drug Reactions

No specific measures for management of specific AEs or adverse drug reactions are proposed at this stage. Adverse drug reactions should be treated symptomatically. Standard medical care will be provided at the study center for all AEs encountered during the study.

For details on the management of AEs and adverse drug reactions, see Section 7.4.1.6.

6.6 Packaging and Labeling of the Investigational Medicinal Product

Packaging and labeling will be in accordance with Manufacture of Investigational Medicinal Products (Annex 13, Volume 4), applicable local regulatory requirements, and applicable Good Manufacturing Practice Guidelines.

Tepotinib tablets will be supplied in aluminum-aluminum blisters. The blisters will be packed in a suitable carton box labeled with (but not limited to) the following required information: study number, number of tablets per box, storage conditions, the words "Caution: New Drug – Limited by Federal (or United States) law to investigational use", batch number, and the Sponsor's name.

6.7 Preparation, Handling, and Storage of the Investigational Medicinal Product

The pharmacy or designee will receive tepotinib labeled and packaged according to the local regulatory requirements and the storage requirements. Tepotinib is formulated as tablets, and is ready for use. The responsible pharmacist or designee will dispense a single dose of tepotinib for administration to the subject during the IMP administration visit. Detailed guidance will be provided in the pharmacy manual.

The IMP supplies will be recorded in a drug inventory and stored in a locked cabinet, protected from environmental extremes until used in the study. Tepotinib should be stored at or below 25°C. Any deviations from the recommended storage conditions should immediately be reported to the Sponsor specified in the pharmacy manual, and the medication should not be used until authorization has been received from the Sponsor.

6.8 Investigational Medicinal Product Accountability

The Investigator (or designee) is responsible for ensuring tepotinib (IMP) accountability, including reconciliation of drugs and maintenance of records.

- Upon receipt of the IMP, the responsible person will check for accurate delivery and acknowledge receipt by signing or initialing and dating the appropriate documentation and returning it to the location specified. A copy will be archived for the Investigator Site File
- The dispensing of the IMP will be recorded on the appropriate drug accountability forms so that accurate records will be available for verification at each monitoring visit
- Study center IMP accountability records will include the following:
 - Confirmation of IMP receipt, in good condition and in the defined temperature range
 - The inventory of IMP provided for the clinical study and prepared at the center
 - The use of each dose by each subject
 - The disposition (including return, if applicable) of any unused IMP
 - Dates, quantities, batch numbers, kit numbers, expiry dates, and the individual subject study numbers.

The study center should maintain records, which adequately document that subjects were provided the doses specified in this protocol, and all IMPs provided were fully reconciled.

Unused IMP must not be discarded or used for any purpose other than the present study. No IMP that is dispensed to a subject may be redispensed to a different subject.

A Study Monitor will periodically collect the IMP accountability forms.

At the conclusion or termination of this trial, all used and unused IMP kits will be destroyed at the trial site according to local regulations and institutional guidelines. All used and unused medications will be carefully recorded and documented before destruction.

6.9 Assessment of Investigational Medicinal Product Compliance

The IMP will be administered by the study center staff within the confines of the study center. A mouth and hand check will be performed after administration of the IMP to ensure that the dose has been swallowed.

6.10 Blinding

Blinding is not applicable. (Note: the bioanalytical assay will be performed without knowledge of hepatic function group information. Access to hepatic function group information will be restricted and defined in a Data Access Plan).

Emergency Unblinding

Not applicable

6.12 Treatment of Overdose

An overdose is defined as any dose greater than the highest daily dose included in a clinical study protocol or planned for an individual subject enrolled in the study. Even if it does not meet other criteria for an SAE, any overdose must be recorded in the study medication section of the eCRF and reported to Drug Safety in an expedited manner using the SAE Report Form, and following the procedure in Section 7.4.

The effects of an overdose are unknown, and therefore no standard treatment is currently established. In the event of an overdose, the Investigator or treating physician should use appropriate clinical judgement for the management of any clinical symptoms or evaluation results.

6.13 Medical Care of Subjects after End of Study

Since this is not an interventional study, medical care of subjects after the End of Study visit is not applicable. After a subject has completed the study or has withdrawn early, follow up treatment will only be administered if required due to an ongoing TEAE.

7 Study Procedures and Assessments

Prior to performing any study assessments, the Investigator will ensure that the subject has provided written informed consent according to the procedure described in Section 9.2.

A subject identifier (see Section 9.3) will be assigned for each subject for who provided written informed consent.

Subjects are not allowed to have participated in a clinical study within the 30 days prior to administration of IMP.

All efforts should be made to perform assessments as close as possible to the scheduled timepoints.

Subjects will be admitted to the study center on Day -1 and remain resident at the study center until the morning of Day 4, after completion of the Day 4 assessments.

When several procedures are scheduled at the same theoretical time, the following sequence should be followed: 12-lead ECG followed by vital signs before the specified timepoint, preceding the PK sampling which will be performed at the specified timepoint. Therefore, assessments not performed at the exact timepoint are not to be considered protocol deviations as long as the actual collection date and time is recorded. Every effort should be made to perform assessments at the appropriate timepoint.

7.1 Schedule of Assessments

The detailed Schedule of Assessments for Part 1 and Part 2 are provided in Table 1.

7.1.1 Screening Visit

Screening of the subjects will take place within 2 to 28 days prior to Day 1. At the start of Screening, candidates for the study will be fully informed about the nature of the study and the possible risks, and will receive a copy of the subject information and informed consent form for review.

After written informed consent is obtained for all procedures in the study, subjects will be evaluated for entry into the study according to the inclusion and exclusion criteria (Section 5.3). Screening procedures specified in the Schedule of Assessments for Part 1 and Part 2 (Table 1) must be performed and evaluated during Days -28 to -2.

If the subject meets all of the protocol inclusion criteria and none of the exclusion criteria, he/she will be considered as eligible and will be enrolled into the clinical study.

Subjects who fail to meet the protocol specified criteria for dosing, who withdraw from the study or who withdraw their consent in the Screening period are considered screening failures. The following data, as a minimum, should be recorded for these subjects: date of informed consent, inclusion/exclusion criteria, demographics (including age, sex (gender), weight, and height), AEs (if any) from the date of informed consent until the subject is considered a screen failure by the Investigator, reason for screening failure, and the Investigator's signature. Rescreening for eligibility of subjects who failed the initial screening will be allowed once per subject within the 28 day Screening period.

7.1.2 Treatment Period

A review and update of the subject's medical history, possible AEs, concomitant medication use and inclusion/exclusion criteria, to ensure the subject remains eligible for participation in the study,

should be performed prior to admission to the study center, on Day -1. Eligible subjects will participate in Part 1 of the study. Subjects will receive their respective IMP dose on Day 1. Subjects will be discharged from the study center on the morning of Day 4, after completion of the Day 4 assessments.

Part 2 of the study is optional. Details are provided in Section 5.1.

Specific assessments to be performed during the treatment periods are presented in the Schedule of Assessments (Table 1).

7.1.3 End of Study Visit/Early Termination Visit

Healthy subjects will partake in the End of Study visit on Day 15 and hepatic impaired subjects will partake in the End of Study visit on Day 22. Assessments at the End of Study visit are specified in the Schedule of Assessments for Part 1 and Part 2 (Table 1). Subjects who discontinue from the study for any reason prior to the End of Study visit must undergo an Early Termination visit immediately upon discontinuation. Assessments at the Early Termination visit are the same as for the End of Study visit.

